### 5.3. Vital Signs and Physical Examination Findings

Similarly, only vital signs abnormalities emerging after vaccination will be tabulated by worst abnormality grade.

**For cohort 0**, heart rate (beats per minutes, bpm), respiratory rate (breaths per minute), systolic blood pressure (mmHg) and diastolic blood pressure (mmHg) will be collected. The respective vital signs abnormalities are defined in [Table 3](#). Moreover, only the vital signs values will be used, no clinical interpretations, therefore, grade 3 and 4 is shown combined as grade 4 always requires clinical interpretation.

**Table 3: Vital Signs Toxicity table for Cohort 0**

Vital Signs	Grade 1	Grade 2	Grade 3/4
Tachycardia – beats (HR) per minute	101 – 115	116 – 130	>130
Bradycardia – beats (HR) per minute	50 – 54	45 – 49	< 45
Hypertension (systolic) - mm Hg	141 – 150	151 – 155	>155
Hypertension (diastolic) - mm Hg	91 – 95	96 – 100	>100
Hypotension (systolic) - mm Hg	85 – 89	80 – 84	< 80
Respiratory Rate - breaths per minute	17-20	21-25	>25

**For Cohort 1**, heart rate (beats per minutes, bpm) and respiratory rate (breaths per minute) will be collected. Since no vital sign toxicity table is available for toddlers any abnormality will be recorded as an AE, by the investigator. Only respiratory rates will be summarized with descriptive statistics.

For both cohorts, temperature (diary, on site assessments) will be allocated to predefined temperature intervals (from 37.5° C until 40°C, in steps of half degree increments; eg <37.5, 37.5-<38, 38-<38.5, ... >40). Tables will show the maximum temperature for both diary and onsite assessments separately. A listing of subjects with fever according to the FDA grading table will also be provided.

Respiratory rates will also be summarized descriptively for both Cohorts.

Any abnormal physical examination result will be documented as AEs, by the investigator.

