**A: Tables for Clinical Abnormalities**

Local Reaction to Injectable Product	Mild (Grade 1)	Moderate (Grade 2)	Severe (Grade 3)	Potentially Life-threatening (Grade 4)
Pain	Does not interfere with activity	Repeated use of non-narcotic pain reliever > 24 hours or interferes with activity	Any use of narcotic pain reliever or prevents daily activity	Emergency room visit or hospitalization
Tenderness	Mild discomfort to Touch	Discomfort with Movement	Significant discomfort at rest	Emergency room visit or Hospitalization
Erythema/redness*	2.5 – 5 cm	5.1 – 10 cm	> 10 cm	Necrosis or exfoliative dermatitis
Induration/swelling**	2.5 – 5 cm and does not interfere with activity	5.1 – 10 cm or interferes with activity	> 10 cm or prevents daily activity	Necrosis

\* In addition to grading the measured local reaction at the greatest single diameter, the measurement should be recorded as a continuous variable.

\*\* Induration/Swelling should be evaluated and graded using the functional scale as well as the actual measurement.

Vital Signs *	Mild (Grade 1)	Moderate (Grade 2)	Severe (Grade 3)	Potentially Life-threatening (Grade 4)
Fever** (°C)	38.0 – 38.4	38.5 – 38.9	39.0 – 40	>40
Fever** (°F)	100.4 – 101.1	101.2 – 102.0	102.1 – 104	>104
Tachycardia - beats per minute	101 – 115	116 – 130	>130	Emergency room visit or hospitalization for arrhythmia
Bradycardia - beats per minute***	50 – 54	45 – 49	< 45	Emergency room visit or hospitalization for arrhythmia
Hypertension (systolic) - mm Hg	141 – 150	151 – 155	>155	Emergency room visit or hospitalization for malignant hypertension
Hypertension (diastolic) - mm Hg	91 – 95	96 – 100	>100	Emergency room visit or hospitalization for malignant hypertension
Hypotension (systolic) - mm Hg	85 – 89	80 – 84	< 80	Emergency room visit or hospitalization for hypotensive shock
Respiratory Rate - breaths per minute	17 – 20	21 – 25	>25	Intubation

\* Subject should be at rest for all vital sign measurements.

\*\* Oral temperature; no recent hot or cold beverages or smoking.

\*\*\* When resting heart rate is between 60 - 100 beats per minute. Use clinical judgment when characterizing bradycardia among some healthy subject populations, for example, conditioned athletes.

Systemic (General)	Mild (Grade 1)	Moderate (Grade 2)	Severe (Grade 3)	Potentially Life-threatening (Grade 4)

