### **5.2. Clinical Laboratory Tests**

For laboratory safety parameters, only abnormalities emerging after vaccination will be tabulated by worst abnormality grade using the FDA table in [Attachment 1](#).

An abnormality (toxicity grade or abnormality based on normal ranges) will be considered as emerging in a particular period if it is worse than the baseline value. If the baseline is missing, the abnormality is always considered emerging. A shift from ‘abnormally low’ at baseline to ‘abnormally high’ post baseline (or vice versa) is also emerging. In case a laboratory test result is censored (no numeric value is available, but only a verbatim term) then a numeric value will be imputed by a value exceeding the cut-off value with one unit. (<x: subtract 1 unit from x, >x: add 1 unit to x; <3.45 is imputed with 3.44).

In case no toxicity grades are defined for a test, the abnormalities (above/below normal range) will be used. In determining toxicity grades, the following rules are applied:

- worst grades/abnormalities are determined over the whole observational period for each trial period separately, including all post-baseline measurements of that period.
- The abnormalities ‘abnormally low’ and ‘abnormally high’ are considered equally important, i.e. if a subject has as well an abnormally low as an abnormally high value post-baseline, both abnormalities are shown in the tables. (This means that the sum of the percentages can be more than 100%)
- Note: as the grading scale for some parameters in the grading table has some gaps (zones where no toxicity grade definition exists), laboratory results falling in these zones will be allocated to the adjacent worst-case grade.
- If a lab value falls within the grading as specified in the grading table but also within the local lab normal limits, the value is considered as normal.

For the grades, no distinction will be made between test results of samples obtained under fasting and under non-fasting conditions: in case limits under fasting and non-fasting conditions differ, the limits of the conditions (fasting/non-fasting) of scheduled visits as planned in the CTP will always be used, also for samples obtained under a different condition (e.g. samples of withdrawal visits).

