\* Subject should be at rest for all vital sign measurements.

\*\* Oral temperature; no recent hot or cold beverages or smoking.

\*\*\* When resting heart rate is between 60 - 100 beats per minute. Use clinical judgement when characterizing bradycardia among some healthy subject populations, for example, conditioned athletes.

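### SAP Table 3 omits the 60–100 bpm resting-rate condition that both Attachment 1 tables attach to bradycardia, so adults with baseline below 60 bpm whose grade worsens enter the Cohort 0 table

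*SAP*

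**What the plan says.** SAP 5.3 covers the Cohort 0 heart rate, respiratory rate and blood pressure tables. On what counts as abnormal it says "The respective vital signs abnormalities are defined in" Table 3. The bradycardia row of that table is "Bradycardia – beats (HR) per minute 50 – 54 45 – 49 < 45" for Grades 1, 2 and 3/4, with no footnote. The section explains that "only the vital signs values will be used, no clinical interpretations", and gives this as the reason for merging Grades 3 and 4.

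Protocol Attachment 1, part A, has the same three cut-offs, with a footnote on bradycardia: "When resting heart rate is between 60 - 100 beats per minute. Use clinical judgment when characterizing bradycardia among some healthy subject populations". The vital-signs table in SAP Attachment 1 repeats it: "When resting heart rate is between 60 - 100 beats per minute. Use clinical judgement when characterizing bradycardia among some healthy subject populations".

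Two further rules decide what reaches the table. SAP 5.3 says "only vital signs abnormalities emerging after vaccination will be tabulated by worst abnormality grade". It opens by referring back to the laboratory rule in SAP 5.2, where an abnormality "will be considered as emerging in a particular period if it is worse than the baseline value", and is always emerging if baseline is missing. SAP 2.1 defines baseline as the last assessment before the first vaccination.

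**The concern.** The same cut-offs carry a numeric restriction in two places and none in the place that drives the analysis. An adult whose usual resting pulse is below 60 bpm is outside the bradycardia scale in both attachments but inside it in Table 3. SAP 1.6, which lists changes to planned analyses, does not mention the difference.

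At stake is the reading of one safety table in a very small cohort. An entry would be labelled as bradycardia emerging after vaccination in someone whom the adopted scale would leave ungraded. With 8 active and 4 placebo adults, one such entry is visible as a percentage and can look like a difference between groups.

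**Working it through.** The plan states no figure to reproduce here; the check is a comparison of rules.

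**Inputs.** Table 3 grades: 55 bpm or higher, none; 50–54, Grade 1; 45–49, Grade 2; below 45, Grade 3/4. Emergence: SAP 5.2, carried into 5.3. Condition: resting rate 60–100 bpm (both Attachment 1 tables), applied below to the baseline value, which is an interpretation. Cohort 0: 8 active and 4 placebo (SAP Table 1).

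**Does the values-only rule explain the omission?** The footnote has two parts. The second calls for clinical judgement and falls under that rule. The first is a numeric range that can be checked against recorded data. Vital signs are measured before the first dose (Protocol 9.1.3.2.1), and heart rate is taken after at least 5 minutes of rest (Protocol 9.2.3.3). So the rule explains losing the second part only.

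**Which heart-rate pairs are affected?**

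| Baseline | Post-dose | Table 3 grade | Emerging, by grade | Emerging, by raw value | Graded if baseline must be 60–100 |
|---|---|---|---|---|---|
| 65 | 54 | none to 1 | yes | yes | yes |
| 58 | 54 | none to 1 | yes | yes | no |
| 57 | 53 | none to 1 | yes | yes | no |
| 52 | 49 | 1 to 2 | yes | yes | no |
| 52 | 50 | 1 to 1 | no | yes | no |
| 47 | 45 | 2 to 2 | no | yes | no |
| 52 | 54 | 1 to 1 | no | no | no |

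Read by grade, the extra entries are baseline 55–59 falling to 54 or lower, and baseline 54 or lower falling a grade. Read by raw value, small falls within a grade are added. Two edge cases remain: a missing baseline counts as emerging, and the condition would also exclude a baseline above 100.

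**Size of one entry.** 1/8 = 12.5% of the active group; 1/4 = 25% of placebo.

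**Frequency.** The documents give no heart-rate distribution. As an illustration only, assume normally distributed heart rates with mean 64, 68 or 72 bpm, between- and within-subject SDs of 8 and 5, 10 and 5, or 10 and 7, one baseline and four post-dose readings, and no vaccine effect. Simulating 400,000 subjects per setting and applying emergence by grade, the expected number of the 12 adults with emerging bradycardia is 0.78 to 3.75 under Table 3 and 0.42 to 1.75 with the condition on baseline. The within-setting difference runs from 0.78 − 0.42 = 0.36 to 3.75 − 1.75 = 2.00 adults. That more than fivefold spread comes entirely from the assumptions.

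**The case against.** The best defence is that the protocol's own vital-sign analysis has no baseline condition. Protocol 11.7 asks only for the percentage of subjects with heart rates beyond clinically relevant limits, and Protocol 12.1.3 uses Attachment 1 to grade adverse events. On that view Table 3 is a plain values-based summary, and keeping every low reading visible is a cautious choice in a safety run-in. It stands that Table 3 does not breach 11.7, and that simple removal would hide a real fall such as 58 to 44. It does not remove the mismatch: 11.7 names no limits, and Table 3 takes its cut-offs from the same scale without their condition or a stated reason.

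Neither attachment says which measurement is the resting rate. It cannot be the graded reading, since 50–54 lies outside 60–100. Using the last pre-dose value is reasonable, but the SAP would have to declare it. One baseline reading is also noisy, so the condition does not clear the table of chance entries; the illustration leaves 0.42 to 1.75.

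A reader might infer that every adult with a naturally low pulse will be tabulated. The emergence filter rules that out. A reader might also infer a false signal in the check of the new formulation buffer. Protocol 3.1 lists adverse events, serious adverse events and, after the first dose, safety laboratory data as inputs to the Cohort 0 reviews. It does not list graded vital-sign tables. No pausing rule in Protocol 11.10 counts them, and no formal group comparison is planned (SAP 5).

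**Conclusion.** The inconsistency is real and minor. SAP Table 3 differs from Protocol Attachment 1 and from the SAP's own Attachment 1, and the values-only sentence accounts for just the clinical-judgement half of the omitted footnote. The consequence is a possible over-count among adults with baseline below 60 bpm whose grade worsens, widened to smaller falls if worse is read on the raw value. The same rule applies to both groups.

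The conclusion rests on taking baseline as the resting rate and on the laboratory definition of emergence carrying over to vital signs. The simulated counts are conditional on assumed inputs and do not establish how often this would happen.

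**What to change.** Reconcile Table 3 with Attachment 1 by three short additions to SAP 5.3:

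- A footnote that bradycardia grades apply to subjects whose baseline heart rate is 60–100 bpm, stating that baseline (the last pre-dose value) serves as the operational resting rate.
- A separate line or listing for subjects with baseline below 60 bpm who reach 54 bpm or lower, with the values and change from baseline, so that real falls stay visible.
- A statement that worse than baseline means a worse grade.

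The cost is a footnote, a sentence and a small amount of programming on data already collected; listings by phase and time point are already planned (SAP 2.1). The drawback is that falls from a baseline below 60 leave the graded counts, which is why the separate display is part of the change.

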#### **9.2.3.3. Vital Signs**

Blood pressure (Cohort 0 only) and pulse/heart rate measurements should be preceded by at least 5 minutes of rest in a quiet setting without distractions (eg, television, cell phones):

- Heart rate (beats per minutes, bpm), respiratory rate (breaths per minute), systolic blood pressure (mmHg) and diastolic blood pressure (mmHg)
- Body temperature (oral route recommended for Cohort 0, rectal or axillary route recommended for Cohort 1)

Confirmatory vital signs measurement can be performed if inconsistent with a prior measurement. If any clinically significant changes in vital signs are noted, they will be reported as AEs and followed to resolution, or until reaching a clinically stable endpoint.

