### **Clinical Laboratory Tests (Cohort 0 Only)**

Laboratory abnormalities will be determined according to the FDA Guidance document (see [Attachment 1](#)), or in accordance with the normal ranges for the clinical laboratory parameter if no grades are available. If a laboratory value falls within the grading as specified in the FDA table, but also within the laboratory normal limits, the value is considered as normal.

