### **Vital Signs**

A tabulation of the distribution of temperatures per half degree intervals will be provided. For heart rate and respiratory rate, the percentage of subjects with values beyond clinically relevant limits will be summarized.

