## **1.6. Changes to planned analyses**

Two addition interim analyses for Cohort 1 have been added, for the purpose of informing future vaccine-related decisions in a timely manner. The first interim analysis will be performed when 12 subjects have reached Day 8, and the second one when at least 12 subjects have reached Day 29. Given that the first interim analysis coincides with the planned IDMC analysis, the IDMC members will receive immediately unblinded at the group level safety results instead of blinded, as specified in the CTP. That way the IDMC and the study team will possess the same information regarding safety. Moreover, the conduct of the planned interim analysis, when at least 24 subjects of Cohort 1 have reached Day 29 (28 days post-Dose 1) or discontinued earlier, will be dependent on the outcome of the previous interim analyses and is at the discretion of the sponsor.

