### 5.1. Adverse Events (AE)

#### 5.1.1. Definitions

Solicited AEs shown in the tables are extracted from the diary pages of the CRF. For unsolicited AEs, only the AEs starting (grade and/or relation) within the 28-day period following each vaccination will be presented in the safety tables except for SAE, which will be captured and tabulated in the outputs covering the whole study period. All other collected unsolicited adverse events will be presented through listings.

Solicited local AEs will be by definition considered as related to the study vaccine.

The severity of the AEs will be classified as grade 1 to 4. Solicited events that are graded less than grade 1, are not considered as AE. In case no grades are available, the grading of the solicited events will occur according to the grading list in [Attachment 1](#).

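### For Cohort 1, SAP 5.3 replaces protocol 11.7's out-of-limits percentages for heart rate and respiratory rate with AE reporting and a respiratory-rate summary, and SAP 1.6 does not list the change

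*SAP*

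**What the plan says.** Protocol 11.7, under Vital Signs, plans a tabulation of temperature in half-degree steps and then adds: "For heart rate and respiratory rate, the percentage of subjects with values beyond clinically relevant limits will be summarized". No cohort is named. The laboratory paragraph just before it is headed "Clinical Laboratory Tests (Cohort 0 Only)", so this section marks a restriction where one is meant.

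SAP 5.3 treats the cohorts differently. Adults get emerging abnormalities in heart rate, respiratory rate and blood pressure, graded by SAP Table 3. For toddlers, "heart rate (beats per minutes, bpm) and respiratory rate (breaths per minute) will be collected", followed by the reason and the substitute: "Since no vital sign toxicity table is available for toddlers any abnormality will be recorded as an AE, by the investigator". The next sentence is "Only respiratory rates will be summarized with descriptive statistics". Temperature is tabulated in intervals for both cohorts.

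Protocol 9.2.3.3 words the AE route differently: "If any clinically significant changes in vital signs are noted, they will be reported as AEs".

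SAP 1.6 opens with "Two addition interim analyses for Cohort 1 have been added, for the purpose of informing future vaccine-related decisions in a timely manner". The rest of it covers the IDMC receiving group-level results and the now optional 24-subject interim analysis. Vital signs do not appear.

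**The concern.** Toddler safety and tolerability is a primary objective, and Cohort 1 has no safety laboratory tests. Against that background, the SAP drops a by-group summary that the protocol names and does not record it as a change.

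An AE count and a summary of measured values answer different questions. An investigator judges one blinded child at a time. A reading outside a limit that the investigator does not consider clinically significant would count in the protocol's percentage but need not become an AE under protocol 9.2.3.3. A modest shift in one group, with no single reading remarkable, shows only when values are set out by group.

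**Working it through.** The plan gives no figure to reproduce here, so the check is a comparison of texts, with a small count for scale.

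**Heart rate and respiratory rate, protocol 11.7 against SAP 5.3, Cohort 1**

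| Parameter | Protocol 11.7 | SAP 5.3, toddlers |
|---|---|---|
| Temperature | Half-degree distribution | Kept, in half-degree intervals |
| Respiratory rate | Percentage outside limits | Descriptive statistics instead |
| Heart rate | Percentage outside limits | No summary; AE route only |

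Two percentages are therefore gone. One parameter keeps a summary in another form, and one keeps none.

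**Does the SAP's reason account for this?**

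1. The lack of a toddler grading table applies equally to heart rate and respiratory rate. Protocol Attachment 2 and SAP Attachment 2 grade fever but neither of these two. Respiratory rate is summarised all the same.
2. Descriptive statistics need no grades. SAP 5 already names those for continuous safety variables (number of observations, median, quartiles, minimum, maximum), and SAP 2.1 defines baseline.
3. For laboratory tests without grades, SAP 5.2 falls back on values above or below the normal range. SAP 5.3 offers toddlers no comparable fallback.
4. The reason does bear on the percentages. Neither document says what limits are clinically relevant for a toddler, so those percentages cannot be produced as the plan stands.

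**What does the AE route retain?** Under SAP 5.1.1, for unsolicited events, "only the AEs starting (grade and/or relation) within the 28-day period following each vaccination will be presented in the safety tables"; SAEs are tabulated over the whole study and other events are listed. Apart from Days 57 and 211, where vital signs are discretionary, the planned post-dose readings fall close enough to a vaccination that this window costs little. The loss comes from the judgement needed to turn a reading into an AE, and the two documents set that threshold differently.

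**Scale**

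- Cohort 1 share of planned subjects: 36 / (12 + 36) = 36/48 = 75%.
- Planned heart-rate readings per toddler, from the visit descriptions in protocol 9.1.4: screening (1), Day 1 before and after dosing (2), Day 8 (1), Day 29 before and after dosing (2), Day 36 (1), giving 7.
- Of these, screening and pre-dose Day 1 precede vaccination, leaving 7 − 2 = 5.
- Over 36 toddlers: 36 × 7 = 252 readings, of which 36 × 2 = 72 are baseline and 36 × 5 = 180 follow the first dose.

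The count assumes full attendance and that the vital signs documented after observation include heart rate. Some symbols in the Time and Events Schedule are unreadable, so it rests on the visit text. It measures data left without a summary, not an effect on any result.

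**The case against.** The case for leaving the SAP alone has real content.

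- **The SAP states a reason and a substitute.** Abnormalities go to AE reporting, AEs are tabulated or listed, and SAP 2.1 plans listings by phase and time point. This stands. A reader might infer that toddler heart-rate data go wholly unanalysed, and the documents do not support that.
- **Protocol 11 calls itself general and leaves detail to the SAP.** True, but naming two parameters and a statistic is a specific plan. Replacing it belongs in SAP 1.6, the section kept for such changes. The separate data presentation specifications might add a table, but the SAP's word "Only respiratory rates will be summarized with descriptive statistics" points the other way.
- **A shift inside the limits would not show in the protocol's percentage either.** Correct. Summaries by visit and change from baseline go beyond protocol 11.7; they are recommended because they are cheap and need no limits. The percentage would still catch readings outside limits that were not judged clinically significant.
- **Vital signs are not the only objective measurements in toddlers.** A reader might think so because there are no laboratory tests. But temperature is tabulated, and erythema and swelling are measured by ruler. Nor is it accurate to say that half the promised summary is removed, as the table above shows.
- **Nothing is tested.** All safety analysis is descriptive and no primary endpoint is a vital-sign summary. This limits the weight of the point but does not remove the mismatch.

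**Conclusion.** The point holds as a minor, undeclared departure from the protocol. For 36 of 48 planned subjects, the SAP drops both out-of-limits percentages and leaves heart rate with no summary of its measured values. Its reason explains why the percentages are hard to produce, but not why heart rate lacks the descriptive summary given to respiratory rate. The AE route preserves what investigators report, under a threshold worded one way in SAP 5.3 and another in protocol 9.2.3.3.

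This rests on reading protocol 11.7 as covering both cohorts, which the explicit restriction on its laboratory paragraph supports. Nothing in the documents suggests that a heart-rate signal exists or was missed, and no planned conclusion would change.

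**What to change.** - **SAP 5.3, Cohort 1:** add a descriptive heart-rate summary next to respiratory rate, giving values and change from baseline by group and visit, with the statistics already named in SAP 5.
- **Out-of-limits percentages:** the sponsor should either pre-specify the toddler limits it regards as clinically relevant, for both parameters, or record in SAP 1.6 that the percentages will not be produced and why. The protocol amendment log shows that group-level interim results have already been reviewed, so any limits should be set without reference to the trial's own values by group.
- **AE wording:** reconcile SAP 5.3 with protocol 9.2.3.3 on which vital-sign findings are reported as AEs. Which rule applies is for the sponsor to settle.

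The cost is one descriptive table from data already collected and a short entry in SAP 1.6. Choosing limits would take additional clinical input, but the heart-rate table does not depend on it.
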